3. Admitted to Bethesda North Mom Baby Unit
4. Postpartum
5. Experiencing urinary retention – defined as meeting at least one of the following criteria:
 - More than 6 hours after delivery or foley catheter removal without being able to spontaneously void
 - Symptomatic urinary retention without being able to spontaneously void
 - Change in fundal height or position without being able to spontaneously void
6. Bladder scan showing bladder containing 400mL or more urine

Exclusion Criteria

1. Allergy to peppermint
2. Asthma
3. Active herpes lesions
4. Seizure disorder
5. Not able to void in toilet (ex: requiring use of bed pan to void)

Sample Size Determination: A power analysis was conducted using G*Power (version 3.1.9.2). The primary outcome variable (resolution of urinary retention) was used with a medium effect size, power of 0.8, and level of significance 0.05. It was determined that 44 patients would be needed in each group, for a total sample size of 88 patients. Therefore, we plan to enroll approximately 100 patients (50 randomized to each group) to allow for missing data and patient withdrawals.

- **Data Collection**

Before the study begins, the study staff will provide education to team members working in the unit involved in patient care. This education will include information about the study design, the intervention, and the inclusion/exclusion criteria.

Patients who meet the inclusion criteria will be approached by a member of the study team. The study team member will describe the study and answer any questions the patient has. If the patient is interested in enrolling in the study, they will be asked to review and sign an Informed Consent and HIPAA Authorization

Form. Name is included on the Informed Consent Document and name and date of birth are included on the HIPAA Authorization.

After the patient provides written informed consent, the study team member will remove the next envelope out of a box of prefilled and sealed opaque envelopes. The envelope will provide the Subject ID number to be used on all study-related documentation and the study Arm that the patient has been randomized to. All 100 envelopes will be filled before the start of the study using a 1:1 computerized randomization generator.

- **Intervention or experimental aspect of the study**

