If the patient is randomized to Arm 1 (intervention group), the study nurse will place 2mL of peppermint oil into the urine collection hat that fits into the toilet bowl. Subjects will sit on the toilet exposing their perineum to the vapor of the oil. The perineum will NOT come into contact with the oil directly. After approximately 10 minutes, the nurse will remove the patient from the toilet. If spontaneous urination occurred, the nurse will measure the volume of urine obtained in the hat. The nurse will calculate approximate volume of urine remaining in the bladder (bladder scan volume minus volume of urine in collection hat). If approximate volume remaining in the bladder is 200mL or greater, the nurse will perform a second bladder scan and follow standard practice for urinary retention.

If the patient is randomized to Arm 2 (control group), the study nurse will place 2mL of mineral oil into the urine collection hat that fits into the toilet bowl. Subjects will sit on the toilet exposing their perineum to the vapor of the oil. The perineum will NOT come into contact with the oil directly. After approximately 10 minutes, the nurse will remove the patient from the toilet. If spontaneous urination occurred, the nurse will measure the volume of urine obtained in the hat. The nurse will calculate approximate volume of urine remaining in the bladder (bladder scan volume minus volume of urine in collection hat). If approximate volume remaining in the bladder is 200mL or greater, the nurse will perform a second bladder scan and follow standard practice for urinary retention.

The voiding procedure using the oil and urine collection hat will be performed only one time with each participant. The study participants won't be explicitly told which group they were randomized into, but the investigators do not consider the subjects to be blinded to group assignment since the smell of the oil will be detectable.

A data collection form will be in the randomization envelope. Data will be recorded directly on this form and collected by a study team member after completion of the study.

Independent variable:

- Whether patient sat on toilet for full 10 minutes

Dependent variables:

- Primary outcome variable – Whether patient spontaneously voided
- Secondary outcome variables:
 - Time that patient spontaneously voided
 - Volume of spontaneous void
 - Whether patient required urinary catheterization or not
 - Patient reported satisfaction with intervention

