Potential confounding variables:

- If patient required a second bladder scan, volume of that scan
- Patient's self-reported pain level
- Method of delivery – vaginal or cesarean section
- Whether patient received an epidural or not
- Type of repair
- Whether it was an assisted birth
- Whether patient received duramorph
- Whether patient had foley catheter during stay

- **Statistical Analysis**

Data will be recorded on paper data collection forms with only subject ID and no identifiers. Data from these forms will be entered into a password protected database. Only study team members will have access to the database. No personal information will be entered into the electronic database. Data will undergo range checks when entered in the database, and quality control procedures will be performed to ensure accuracy of the data in the electronic database.

Statistical analyses will be performed using Intellectus Statistics statistical software. Descriptive statistics (frequencies for categorical data; means and standard deviations and ranges for continuous data) will be used to describe the sample. The following analyses will be performed to address each hypothesis:

Hypothesis 1: Postpartum patients with urinary retention who are exposed to peppermint oil will experience a higher frequency of resolution of urinary retention compared to postpartum patients with urinary retention not exposed to peppermint oil.

To compare the effects of the intervention, a Chi Square test will be used to compare occurrence of resolution of urinary retention for patients who received

peppermint oil to patients who did not receive peppermint oil. A level of significance of $\alpha=0.05$ will be used.

Hypothesis 2: Postpartum patients with urinary retention who are exposed to peppermint oil will experience a shorter time to spontaneous urination compared to postpartum patients with urinary retention not exposed to peppermint oil.

To compare the effects of the intervention, an independent samples t-test will be used to compare mean time to spontaneous urination for patients who received peppermint oil to patients who did not receive peppermint oil. A level of significance of $\alpha=0.05$ will be used.

Hypothesis 3: Postpartum patients with urinary retention who are exposed to peppermint oil will experience an increased volume of spontaneous urine compared to postpartum patients with urinary retention not exposed to peppermint oil.

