To compare the effects of the intervention, an independent samples t-test will be used to compare mean volume of spontaneous urination for patients who received peppermint oil to patients who did not receive peppermint oil. A level of significance of $\alpha=0.05$ will be used.

Hypothesis 4: Postpartum patients with urinary retention who are exposed to peppermint oil will experience a decreased frequency of urinary catheterization compared to postpartum patients with urinary retention not exposed to peppermint oil.

To compare the effects of the intervention, a Chi Square test will be used to compare occurrence of urinary catheterization for patients who received peppermint oil to patients who did not receive peppermint oil. A level of significance of $\alpha=0.05$ will be used.

Hypothesis 5: Postpartum patients with urinary retention who are exposed to peppermint oil will experience increased patient satisfaction compared to postpartum patients with urinary retention not exposed to peppermint oil.

To compare the effects of the intervention, a Mann Whitney U test will be used to compare patient satisfaction for patients who received peppermint oil to patients who did not receive peppermint oil. A level of significance of $\alpha=0.05$ will be used.

Ethical Considerations

- **Informed consent**

All study staff will complete CITI training. A study staff member will meet with potentially eligible patients and describe the study and answer any questions. If the patient is interested and meets all the inclusion/exclusion criteria, the study staff will review the *Informed Consent and HIPAA Authorization Form* and obtain written informed consent. Patients will receive a copy of their signed Informed Consent and HIPAA Authorization form.

Informed Consent and HIPAA Authorization forms will be stored in a locked area that only study staff will have access to. After the study closes, the signed Informed Consent and HIPAA Authorization forms will be boxed and sent to off-site storage and securely stored for 10 years. At that time, the hard copy forms will be shredded.

- **Privacy information**

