Personal identifiers will not be recorded on data collection forms or the electronic database of final data. Hard copy data collection forms will be stored in locked cabinets that only study staff will have access to. Electronic data will be stored on a password-protected folder on the U drive. Only study staff will have access to the electronic study documents. After data analysis and dissemination is completed, hard copy forms will be boxed and sent to secure storage for 10 years at which time they will be shredded. After data analysis and dissemination, electronic data and forms will be de-identified and transferred to a password-protected flash drive which will be sent to secure storage for 10 years at which time it will be destroyed.

Results (8.12.2025)

Between November 3, 2021 and January 29, 2025, 17 patients were enrolled in the research study.

All patients met the following inclusion criteria:

- 18 years old or older
- English speaking
- Admitted to Bethesda North Mom Baby Unit
- Postpartum
- Experiencing urinary retention – defined as meeting at least one of the following criteria:
 - More than 6 hours after delivery or foley catheter removal without being able to spontaneously void
 - Symptomatic urinary retention without being able to spontaneously void
 - Change in fundal height or position without being able to spontaneously void
- Bladder scan showing bladder containing 400mL or more urine

And patients did not have any of the exclusion criteria:

- Allergy to peppermint
- Asthma
- Active herpes lesions
- Seizure disorder
- Not able to void in toilet (ex: requiring use of bed pan to void)

After consenting to participate in the study, participants were randomized (1:1 randomization) to one of two group:

- Intervention Arm: Subjects will be exposed to vapor of peppermint oil (n=10)
- Placebo Arm: Subjects will be exposed to vapor of placebo/mineral oil (n=7)

	Peppermint Oil n=10	Placebo n=7
Scanned Bladder Volume, mL Minimum - Maximum Mean, SD	400 – 941 648.8, 193	424 – 1000 761, 250
Pain Score, 0-10 Minimum - Maximum Mean, SD	0 – 6 2.1, 2	0 – 6.5 2.6, 3

Hypothesis 1:

After 10 minutes of sitting on the hat with the oil (peppermint/mineral), 3 of the participants exposed to peppermint oil voided and 1 of the participants exposed to the placebo voided:

	Voided – Yes	Voided – No
Peppermint Oil	3	7
Placebo	1	6

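### Hypothesis 3 gives non-voiders no volume; if they fall out of the t-test, it compares women selected by the primary outcome and can miss or reverse a real gain in urine passed

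*Combined protocol and SAP*

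**What the plan says.** Hypothesis 3 is a statement about patients: it predicts that women with retention in the peppermint arm "will experience an increased volume of spontaneous urine compared to postpartum patients with urinary retention not exposed to peppermint oil". The endpoint in the list of dependent variables is "Volume of spontaneous void", a secondary outcome.

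The section on the intervention, in the same words for both arms, makes the measurement conditional: "If spontaneous urination occurred, the nurse will measure the volume of urine obtained in the hat". The next step is worded without that condition: "The nurse will calculate approximate volume of urine remaining in the bladder (bladder scan volume minus volume of urine in collection hat").

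The Statistical Analysis section then states that "an independent samples t-test will be used to compare mean volume of spontaneous urination for patients who received peppermint oil" with that for patients who did not receive it, at a significance level of 0.05. It names the groups by exposure. It does not say whether a woman who did not void is entered as 0 mL, left missing or excluded, and the document defines no analysis set for any hypothesis.

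The Results section reports that "3 of the participants exposed to peppermint oil voided and 1 of the participants exposed to the placebo voided", out of 10 and 7 women. It gives results for Hypotheses 1, 4 and 5, and none for Hypothesis 3.

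**The concern.** A woman who does not void has passed 0 mL. That value is known; it is neither missing nor censored. But if volume is recorded only after a void, her volume field is empty, and a standard t-test on that field leaves her out. The comparison is then between women who voided in one arm and women who voided in the other. Voiding is the primary outcome and happens after randomisation, so these two groups are no longer randomised groups.

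This matters for the question Hypothesis 3 asks. If the oil works by making more women void, that gain is removed before the test is run. If the additional voids are smaller than those that would have happened anyway, the mean among voiders falls, and peppermint looks worse although more urine was passed per woman treated.

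**Working it through.** **The plan's own figure.** The sample size rests on the primary outcome, which "was used with a medium effect size, power of 0.8, and level of significance 0.05". Taking medium as w = 0.30 (an assumption; the plan gives no rates), a chi-square test with 1 df and N = 88 has noncentrality 88 × 0.30² = 7.92 and power 0.804. N = 88 is the smallest N that reaches 0.80, so the stated figure reproduces. No power is stated for Hypothesis 3.

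**Inputs.** From the documents: 44 per arm needed, 50 per arm planned; observed voiding 3/10 = 30% and 1/7 = 14%. Assumed: all voided volumes, and the pairs of voiding rates. Two pairs match w = 0.30:
- 14% v 41%: (0.41 − 0.14) / (2√(0.275 × 0.725)) = 0.27 / 0.893 = 0.30
- 35% v 65%: 0.30 / (2√(0.50 × 0.50)) = 0.30

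**What each analysis estimates.** The all-women contrast is p₁m₁ − p₀m₀, where p is the voiding rate and m the mean void. The voider-only contrast is m₁ − m₀.
- 14% v 41%, all voids averaging 300 mL: all women 0.41 × 300 − 0.14 × 300 = 123 − 42 = +81 mL; voiders only 0.
- Same rates, the extra 27% averaging 200 mL: peppermint total 0.14 × 300 + 0.27 × 200 = 96 mL per woman. All women 96 − 42 = +54 mL; voiders only 96/0.41 − 300 = −66 mL.
- 35% v 65%, the extra 30% averaging 200 mL: peppermint total 105 + 60 = 165 mL. All women 165 − 105 = +60 mL; voiders only 165/0.65 − 300 = −46 mL.

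**Simulated rejection rates** (two-sided 0.05; 3,000 to 4,000 trials per scenario in the main runs). Ranges show the spread over independent runs. Rows 1-3 use 44 per arm and SD 100 mL. Rows 4-8 use 50 per arm, gamma-distributed volumes, SD 150 mL and a control void mean of 350 mL. The last two columns count results favouring peppermint.

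| Placebo v peppermint | Gain per woman, mL | Voider-only difference, mL | Voider-only t-test significant | All women, t-test | All women, Mann-Whitney |
|---|---|---|---|---|---|
| 1. 14% v 41%, all voids 300 | +81 | 0 | 2.4-2.6% for peppermint | 77-79% | 81-84% |
| 2. 14% v 41%, extra voids 200 | +54 | −66 | 22-24% against | about 52% | 74% |
| 3. 35% v 65%, extra voids 200 | +60 | −46 | 25-26% against | 44% | 57-58% |
| 4. 35% v 65%, equal voids | +105 | 0 | 2.4% for | 76% | 82% |
| 5. 14% v 30%, equal voids | +55 | 0 | 2.3% for | 42% | 47% |
| 6. 35% v 65%, peppermint voids 300 | +72.5 | −50 | 21% against | 47% | 64% |
| 7. 14% v 30%, peppermint voids 300 | +40 | −50 | 11% against | 29% | 43% |
| 8. 35% v 65%, peppermint voids 400 | +137.5 | +50 | 19% for | 90% | 90% |

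With equal void volumes the voider-only test rejects in favour of peppermint at its false-positive rate of about 2.5%, whatever the gain in voiding. With no effect and 14% voiding in both arms, the all-women Mann-Whitney test rejects in about 5%, so it holds its level.

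**Numbers available.** At 50 per arm and the observed rates, a voider-only test would rest on about 50 × 0.30 = 15 v 50/7 ≈ 7 women. In the completed data it would be 3 v 1: a pooled test has 3 + 1 − 2 = 2 df, and the placebo variance cannot be estimated.

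**The 17 women with zeros.** All women gives 10 v 7 with 17 − 4 = 13 zeros. In the most favourable ordering, all three peppermint voids exceed the placebo void, and Mann-Whitney gives p of about 0.39. An exact argument confirms that no set of volumes could help. Any reallocation that keeps the three peppermint voiders in that arm is at least as favourable to peppermint, so the one-sided permutation p is at least (10 × 9 × 8)/(17 × 16 × 15) = 720/4080 = 0.18. In the placebo direction it is at least 7/17 = 0.41.

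**The case against.** The strongest reply is that the plan never says non-voiders are dropped. A reader might infer that it does, because measurement is conditional on a void. But the analysis sentence groups women by exposure, the hypothesis covers all patients with retention, and the residual-volume calculation only makes sense for a non-voider if the hat holds 0 mL. The data collection form is not in the document and may already record a zero. This stands: exclusion is the likely default, not stated text, and the harm in the voider-only column is conditional on it.

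A reader might also infer that Hypothesis 3 went unreported because only four women voided. The document gives no reason, so that is not supported.

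If zeros were intended, the planned t-test is valid and, in the first scenario, loses only a few points of power. That also stands. The loss is larger when extra voids are smaller (about 52% v 74%), so the choice of test is not only a matter of taste.

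The volumes are assumed, and the reversal needs the further assumption that added voids are smaller; nothing in the document supports or excludes it. The 14% rate is 1 woman in 7, and 14% v 41% is one pair consistent with a medium effect, not the plan's stated target.

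Finally, with most values at zero, the all-women test nearly repeats Hypothesis 1. At 44 per arm, Mann-Whitney agreed with the Hypothesis 1 chi-square decision in 96% of trials in the first scenario, and in 91% and 75% in the two 200 mL scenarios. This is a real limit on what Hypothesis 3 can add.

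**Conclusion.** The concern holds in conditional form. The plan assigns non-voiders no volume and defines no analysis set. If they are left out, which is how the recorded field would behave by default, Hypothesis 3 does not compare randomised groups. It then has almost no chance of detecting a gain that comes from more women voiding (about 2% v 81-84% in the first scenario), and it can point significantly the wrong way if the added voids are smaller (about 22-24% in the second). If zeros were intended, the plan should say so, and the t-test is the weaker choice in most of the scenarios examined.

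The sizes rest on assumed volumes and voiding rates and are illustrative. That a voider-only contrast omits the gain from extra voiders follows from the design, not from those assumptions. The documents do not support saying that the test as written drops every non-voider, or that a misleading Hypothesis 3 result was published: none is reported. Hypothesis 3 is secondary, the sample size of 88 is unaffected, and no conclusion from the 17 women would change.

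**What to change.** In the Hypothesis 3 paragraph, state that all randomised women are analysed by arm, with 0 mL for each woman who did not void during the exposure period. Use the Mann-Whitney test, already planned for Hypothesis 5, or, if the reported effect is the difference in mean mL per randomised woman, a permutation test on means so that test and estimate match. Report volume among voiders descriptively, without a test.

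For a future trial on this template, add a line to the data form to record 0 mL when no void occurs. For the completed trial, enrolment has ended and no new data are needed, because non-voiders are already identified for Hypothesis 1. The 10 v 7 analysis with 13 zeros can be run and should be labelled post hoc. It allows Hypothesis 3 to be reported but cannot reach significance.

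The cost is one sentence in the plan and one line on the form. The drawback is the heavy overlap with Hypothesis 1 when most values are zero, which the report should state.
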